10.3 Adjustments for Multiplicity

To control the overall type 1 error, the primary and key secondary endpoints will be tested at the 0.05 significance level in the pre-specified order of the primary endpoint, key secondary endpoint 1, key secondary endpoint 2, and key secondary endpoint 3. Once one hypothesis test is not significant, the significance of all subsequent tests will not be assessed. The determination of a successful study is based solely on the results of the primary endpoint analysis regardless of the results for the key secondary endpoints.

10.4 Other Secondary Efficacy Variable(s) and Analysis

Data from subjects in the Full Analysis Set that are randomized to Treatment Sequence 1 (A/B) or 2 (B/A) will be used to assess the secondary efficacy endpoints in the evaluation of the efficacy of SC administration of C1 esterase inhibitor [human] liquid for injection compared to placebo. If a subject discontinues during the treatment period, the days of the treatment period will be the days on treatment for that subject; this is equivalent to the last observation carried forward imputation method to impute the missing information following the subject's discontinuation.

Other secondary efficacy variables are listed as following:

- To determine the proportions of subjects with a clinical response to treatment as defined by: Achieving at least a 50%, 70%, 90% and 100% reduction as well as subjects achieving reduction to less than 1 NNA during a treatment period relative to the pretreatment assessment.
- The summary of clinical response to treatment will be repeated using the Per-protocol Set
- Cumulative attack severity: the normalized sum (per month) of the maximum symptom severity recorded for each angioedema attack in a treatment period.
- Cumulative daily severity: the normalized sum (per month) of the severity scores recorded for every day of reported symptoms in a treatment period.
- Number of attack-free days during a treatment period: the normalized number (per month) of attack-free days.
- Number of angioedema attacks requiring acute treatment during a treatment period: the normalized number of angioedema attacks requiring acute treatment.
- Disease activity as measured by the 98-day AAS: the normalized sum of the daily AAS during a treatment period, where the daily AAS is the sum of AAS items per day. Each AAS item is scored between 0 and 3 points, with the minimum and maximum daily AAS ranging between 0 and 15 points.
- Results of the AE-QoL questionnaire: the questionnaire consists of 17 specific questions that are associated with work, physical activity, free time, social relations, and food.
- Number of angioedema attacks requiring icatibant by the number of icatibant injections during the first three attacks of the treatment period.
- Kaplan-Meier estimate of time to initial improvement and time to complete resolution since acute treatment administration by attack order during the treatment period.
- Kaplan-Meier estimate of time to initial improvement and time to complete resolution since onset of attack by attack order during the treatment period.

The treatment differences in clinical responder rates, both of which are defined within treatments, i.e., the difference in the proportions of subjects with a clinical response to C1 INH

or placebo, each of them will be analyzed using McNemar's test for testing equality of proportions of responders within treatments.

Cumulative attack severity, cumulative daily severity, number of attack-free days during a treatment period and the 98-day AAS will be analyzed using a linear mixed effect model with period, sequence, use of prophylactic therapy with C1 INH, which is derived by long-term prevention with C1 INH at randomization, and treatment as fixed effects, and subject nested within sequence as a random effect. If the variance-covariance matrix of random effects is not positive definite, a mixed effect model with the same fixed effects and subject nested within sequence as repeated measurements will be performed instead. The results will be summarized by the point estimate of within-subject treatment differences or response rates and the corresponding 95% CI.

Kaplan-Meier analysis will be performed on all subjects in the Full Analysis Set without censoring. Median, 25%, 75% quartiles and their CI's will be estimated for time to initial improvement / complete resoluction since acute treatment administration / onset of attack.

Summary statistics (n, mean, SD, median, minimum and maximum) will be provided on each dimension and total score of AE-QoL by treatment and visit. A table will be provided summarizing the change from baseline to each visit and the last observation recorded within the treatment period for a subject's response to each dimension and the total score of AE-QoL.

In addition, angioedema attacks will be summarized by the maximum symptom severity of the attack and treatment for all subjects in the Full Analysis Set. Acute angioedema attacks will be summarized by acute therapy, the maximum symptom severity of the attack and treatment for all subjects in the Full Analysis Set.

Cumulative attack severity, cumulative daily severity and number of attack-free days will be plotted by treatment for the subjects who are randomized to the first two treatment sequences (A/B or B/A) in the Full Analysis Set.

Details on derivation of normalized efficacy variables are provided in the Appendix.

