2.2.2 Secondary Objectives

The key secondary objectives are to demonstrate the superior efficacy of SC administration of 2000 IU C1 esterase inhibitor [human] liquid for injection for the prevention of angioedema attacks relative to placebo as measured by:

1. The proportion of subjects meeting the criterion of at least a 50% reduction in the NNA during the 2000 IU C1 esterase inhibitor [human] liquid for injection treatment period relative to the placebo period.
2. The NNA during each treatment period excluding the first 2 weeks.
3. The proportion of subjects meeting the criterion of at least a 50% reduction in the NNA for the 2000 IU C1 esterase inhibitor [human] liquid for injection treatment period relative to the placebo period excluding the first 2 weeks of each treatment period.

Other secondary objectives are:

- To assess the proportion of responders during treatment with 2000 IU C1 esterase inhibitor [human] liquid for injection relative to treatment with placebo, where the proportion of responders is defined as achieving at least a 50% reduction in the NNA during a treatment period relative to the pretreatment assessment (ie, the subject's attack rate without prophylactic treatment)
- To assess the severity of angioedema attacks during treatment with 2000 IU C1 esterase inhibitor [human] liquid for injection relative to treatment with placebo
- To assess the number of attack-free days during treatment with 2000 IU C1 esterase inhibitor [human] liquid for injection relative to treatment with placebo
- To assess the number of angioedema attacks requiring acute treatment during treatment with 2000 IU C1 esterase inhibitor [human] liquid for injection relative to treatment with placebo
- To assess the safety and tolerability of SC administration of 2000 IU C1 esterase inhibitor [human] liquid for injection
- To assess the immunogenicity of SC administration of 2000 IU C1 esterase inhibitor [human] liquid for injection
- To characterize the PK and PD of SC administration of 2000 IU C1 esterase inhibitor [human] liquid for injection
- To assess the clinical response and safety/tolerability of icatibant (Firazyr[®]) for the treatment of acute angioedema attacks (applicable for subjects ≥ 18 years of age)

- To assess disease activity as measured by the Angioedema Activity Score (AAS)
- To evaluate subject experience with self-administration of SC 2000 IU C1 esterase inhibitor [human] liquid for injection

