9.8.2.2 Other Secondary Efficacy Endpoints

Other secondary efficacy endpoints to be evaluated in this study are:

- To determine the proportions of subjects achieving at least a 50% reduction in the NNA during a treatment period relative to the pretreatment assessment.
- Cumulative attack severity. This score is the sum of the maximum symptom severity recorded for each angioedema attack in a treatment period.

- Cumulative daily severity. This score is the sum of the severity scores recorded for every day of reported symptoms in a treatment period.
- Number of attack-free days during a treatment period.
- Number of angioedema attacks requiring acute treatment a treatment period.
- Disease activity as measured by the 98-day AAS. This score is the sum of the daily AAS during a treatment period, where the daily AAS is the sum of AAS items per day.
- Results of the AE-QoL questionnaire.
- Determine the response to icatibant when administered as treatment for an acute angioedema attack by:
 - Time to subject-assessed initial symptom improvement (TISI)
 - Time to subject-assessed complete symptom resolution (TCSR)

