Subjects in the Full Analysis Set (Section 9.7) that are randomized to Treatment Sequence 1 (A/B) or 2 (B/A) will be used to assess the secondary efficacy endpoints in the evaluation of the efficacy of SC administration of C1 esterase inhibitor [human] liquid for injection compared to placebo. The treatment differences in clinical responder rate, both of which are defined within treatments, will be analyzed using McNemar's test for testing equality of proportions of responders within treatments. All other secondary endpoints will be analyzed using a linear mixed effect model with period, sequence, stratification factor (use of prophylactic therapy with C1 INH), and treatment as fixed effects, and subject nested within sequence as a random effect. The results of all secondary efficacy analyses will be summarized by the point estimate of within-subject treatment differences or response rates and the corresponding 95% CI. Descriptive statistics (n, median, 25% and 75% quartiles, and range) will be provided to summarize icatibant-related efficacy endpoints (TISI and TCSR) by treatment and icatibant-treated angioedema attack for all subjects in the Full Analysis Set. Where appropriate (for subjects ≥ 12 to < 18 years of age), other rescue medications used to treat acute angioedema attacks will also be summarized using descriptive statistics. In addition, angioedema attacks will be summarized by the maximum symptom severity and treatment for all subjects in the Full Analysis Set.

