16. CHANGES TO ANALYSES SPECIFIED IN PROTOCOL

Not applicable.

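### SAP 10.4 omits attacks requiring acute treatment from its mixed-model list, although protocol 9.8.2.2 assigns that endpoint to the model and SAP 16 declares no change

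*SAP*

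**What the plan says.** **Protocol.** Section 2.2.2 sets a comparative objective, active relative to placebo: "To assess the number of angioedema attacks requiring acute treatment during treatment with 2000 IU". Section 9.8.2.2 lists the endpoint: "Number of angioedema attacks requiring acute treatment a treatment period". The same section then assigns methods. Responder rates get McNemar's test, and the two icatibant response times (TISI and TCSR) get descriptive statistics. For the rest, "All other secondary endpoints will be analyzed using a linear mixed effect model", using subjects in sequences A/B and B/A. Secondary results are to be reported as within-subject differences or response rates with 95% CIs.

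**SAP.** Section 3.2 keeps the objective. Section 10.4 keeps the endpoint and defines it: "Number of angioedema attacks requiring acute treatment during a treatment period: the normalized number of angioedema attacks requiring acute treatment". Sections 17.2 and 19.1 group it with four other normalized scores, and 19.1 states that the normalized values are the ones to analyse. The model sentence in 10.4 then reads "Cumulative attack severity, cumulative daily severity, number of attack-free days during a treatment period and the 98-day AAS will be analyzed", followed by the same fixed and random effects as in the primary analysis. Section 10.4 also plans a description, over the Full Analysis Set without restriction by sequence: "Acute angioedema attacks will be summarized by acute therapy, the maximum symptom severity of the attack and treatment for all subjects". Section 16, on changes from the protocol, says "Not applicable".

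**The concern.** The protocol states the rule as a catch-all, and the SAP replaces it with a list of named endpoints. An endpoint missing from the list then has no analysis in the document that programmers follow, even though its objective, definition and derivation are all present. Because section 16 declares no change, nothing tells a reader whether the omission was intended.

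At stake is one comparative secondary objective. If the SAP is followed literally, the study report would give no estimate of the treatment difference and no CI for attacks requiring acute treatment. That would be an unexplained departure from the protocol.

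**Working it through.** No power or error-rate calculation applies. The check is a reconciliation of endpoints and methods, plus one count.

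**Step 1: endpoints in protocol 9.8.2.2 against the method each receives.**

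| Endpoint | Protocol method | SAP method |
|---|---|---|
| 50% responder rate against pretreatment | McNemar | McNemar |
| Cumulative attack severity | Mixed model | Mixed model |
| Cumulative daily severity | Mixed model | Mixed model |
| Attack-free days | Mixed model | Mixed model |
| Attacks requiring acute treatment | Mixed model | None assigned |
| 98-day AAS | Mixed model | Mixed model |
| AE-QoL | Mixed model | Descriptive in SAP 10.4; mixed model for change in the HRQoL SAP, 6.4.1 |
| TISI and TCSR | Descriptive | Kaplan-Meier |

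The protocol sends six endpoints to the mixed model. The main SAP models four and the HRQoL SAP models one: 6 − 4 − 1 = 1 left over.

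**Step 2: the SAP against itself.** SAP 17.2 and 19.1 name five normalized secondary endpoints, and the model sentence in 10.4 names four: 5 − 4 = 1. It is the same endpoint as in step 1.

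**Step 3: is it analysed elsewhere in the SAP?**
- McNemar's test in 10.4 is for responder rates.
- Kaplan-Meier in 10.4 is for time to improvement and time to resolution.
- The count of attacks by number of icatibant injections covers the first three attacks only and is a different variable.
- The plots in 10.4 do not include the endpoint.
- Efficacy subgroup analyses (12.5) cover the primary endpoint and key secondary endpoint 1 only.
- The HRQoL SAP does not include it.

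**Step 4: can the descriptive summary stand in?** It counts attacks, not normalized rates per subject, and it covers the whole Full Analysis Set. With the planned numbers (26 A/B, 26 B/A, 14 A/A):

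- Active subject-periods: 26 + 26 + 2 × 14 = 80
- Placebo subject-periods: 26 + 26 = 52
- Ratio: 80 / 52 = 1.54

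If attack rates were equal on both treatments, with no dropout and no period effect, the active column would be expected to hold about 1.54 times as many attacks as the placebo column. SAP 17.1 allows a column layout that separates A/A. Even then the table would have no within-subject difference and no CI.

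**The case against.** The strongest reply is that the comparison is already pre-specified. The protocol's general sentence covers the endpoint. SAP section 1 presents the SAP as a detailed account of the analyses in protocol amendment 4, and section 16 declares no change. Section 10.4 opens by saying that A/B and B/A data will be used to assess the secondary endpoints against placebo, and 19.1 prepares the normalized value for analysis. On this view the omission is a slip in a list.

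Most of that stands, and it sets the size of the point. A reader might infer that the endpoint gets no treatment comparison at all. The documents do not support this, because the protocol commitment remains and the SAP keeps a by-treatment description. The reply does not remove the inconsistency: a closed list has replaced the general rule, and the SAP is what will be programmed.

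Three further inferences should also be resisted:
- **AE-QoL is lost in the same way.** It is missing from the same sentence, but SAP 12.3 refers quality-of-life analyses to a separate plan, and HRQoL SAP 6.4.1 gives AE-QoL a mixed model.
- **This endpoint is less subjective than the severity scores.** Protocol 5.2.1 leaves the need for treatment to the investigator's discretion.
- **The Phase 2 result in protocol Table 6 (−0.56, 95% CI −1.06 to −0.05, p = 0.0315) shows what would be lost.** That result compares 2000 U with 1000 U, both with rHuPH20, in 22 completers. It is not a comparison with placebo.

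**Conclusion.** The point holds as an undeclared inconsistency between protocol and SAP for one secondary endpoint. The protocol requires a mixed-model estimate with a 95% CI; the SAP defines and normalizes the endpoint but assigns it no model, difference, CI or test. It reads as a drafting omission, since nothing in either document gives a reason for dropping the analysis.

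The consequence is small. Under SAP 10.3 the fixed testing order contains only the primary and three key secondary endpoints, and study success rests on the primary alone. The primary conclusion, type I error and sample size are unaffected.

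This rests on the visible text. The table and figure specifications are in a separate document (SAP sections 1 and 18), and the opening of SAP 10.5 was not available to me. Either might mention the endpoint. Neither would make the model sentence in 10.4 consistent with the protocol.

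**What to change.** Before unblinding, add the normalized number of angioedema attacks requiring acute treatment to the mixed-model sentence in SAP 10.4. Report the within-subject treatment difference and 95% CI in sequences A/B and B/A, as for the four endpoints already listed, and check that the table specifications include the output. If the omission was deliberate, declare and justify it in SAP 16 instead.

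The cost is one phrase in the SAP, one table, and one more run of a model that is already programmed. The derivation is already specified in SAP 19.1 and 19.2, and no new data are needed.

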17.11 Handling Missing HAE Attack Data

If there are incomplete attack start/end dates in the collected data, the following imputations will be performed in a sequential order of the incomplete dates within each subject. This is to ensure that multiple identical incomplete dates will be imputed as separate attacks.

- Imputation of start date for an attack:
- If the attack start day is unknown and there is no previous attack in the same month, the first day of the month will be assigned to the missing field.
- If the attack start day is unknown and there is at least one previous attack in the same month, the previous attack end date + 1 will be assigned to the missing field.
- Imputation of end date for an attack:

The imputation of end date for an attack will follow one of the following 3 rules, whichever is the earliest:

- The start date of the current attack + 6 if attack end date is partially or completely missing.
- The start date of the next attack -2 if attack end date is partially or completely missing.
- The last day of the month if attack end date is partially missing with missing day only.

Page 54

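### Kaplan-Meier times to improvement and resolution are run with no censoring, so attacks without an observed event have no valid place in the estimate

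*SAP*

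**What the plan says.** SAP 10.4 lists two pairs of time-to-event summaries among the other secondary variables. One pair runs from treatment: "Kaplan-Meier estimate of time to initial improvement and time to complete resolution since acute treatment administration by attack order during the treatment period". The other runs from onset: "Kaplan-Meier estimate of time to initial improvement and time to complete resolution since onset of attack by attack order during the treatment period". For all four, "Kaplan-Meier analysis will be performed on all subjects in the Full Analysis Set without censoring". The output is descriptive: "Median, 25%, 75% quartiles and their CI's will be estimated for time to initial improvement", and likewise for complete resolution.

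Protocol 7.2.2.4 takes both times from the subject's diary entries for icatibant-treated attacks. Protocol 9.8.2.2 planned only n, median, quartiles and range for these endpoints and did not name Kaplan-Meier. SAP section 16 records no change from the protocol.

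The only relevant missing-data rule is SAP 17.11, which covers attack start and end dates. A missing end date becomes the earliest of three candidates. The first is "The start date of the current attack + 6 if attack end date is partially or completely missing". The second is "The start date of the next attack -2 if attack end date is partially or completely missing". The third is the last day of the month when only the day is missing. Nothing covers a missing time of initial improvement. Nothing says whether an imputed end date feeds time to resolution.

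**The concern.** Kaplan-Meier estimation is useful because it uses the partial information in an observation whose event was not seen. With censoring ruled out, the curve is simply the empirical distribution of the times entered. An attack with no observed event must then be left out, counted as an event when observation stopped, or given an invented time. The SAP does not choose among these.

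Such attacks are foreseeable. The times depend on diary entries. Protocol 5.2.1 allows repeat icatibant and then other therapy when the response is inadequate. Protocol 4.4 and 4.4.1 allow withdrawal at any time, including for lack of efficacy. If the unobserved events tend to be slow ones, the reported quartiles are too short. At stake is the description of response to acute treatment, which serves a stated secondary objective. The comparison of C1 INH with placebo on attack rate is not affected.

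**Working it through.** The documents give no event count, expected median or share of attacks without an event, so there is no planned figure to reproduce. Let q be the share of attacks with no observed event. It is an assumption, ranged from 2% to 30%. Times are taken as exponential unless stated, and results are ratios of reported to true median.

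**Case 1, random loss to follow-up.** With event rate λ and loss rate μ = λq/(1−q), the probability of loss before the event is q. The earlier of the two times is exponential with rate λ + μ = λ/(1−q), whether or not it ended in an event. Dropping the lost attacks, or counting them as events at last observation, therefore gives a ratio of 1−q at every quartile.

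**Case 2, the slowest share q is dropped.** The reported p-quantile is the true p(1−q)-quantile, so the ratio is ln(1−p(1−q))/ln(1−p). For the median at q = 5%: ln(0.525)/ln(0.5) = 0.93. At q = 10%: ln(0.55)/ln(0.5) = 0.86. For the upper quartile at q = 10%: ln(0.325)/ln(0.25) = 0.81.

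**Case 3, missing for reasons unrelated to duration, then dropped.** The ratio is about 1.00.

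| q | Case 1, median | Case 2, median | Case 2, upper quartile |
|---|---|---|---|
| 2% | 0.98 | 0.97 | 0.96 |
| 5% | 0.95 | 0.93 | 0.90 |
| 10% | 0.90 | 0.86 | 0.81 |
| 20% | 0.80 | 0.74 | 0.66 |
| 30% | 0.70 | 0.62 | 0.54 |

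A simulation of 400,000 attacks reproduced Case 1 and Case 3. As a check on shape, log-normal times with an assumed log-SD of 0.8 give Case 2 median ratios of about 0.95 and 0.90 at q = 5% and 10%. That is the mild end of the same range.

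**Resolution, if SAP 17.11 dates are used.** Take log-normal times as above, an assumed true median of 0.5 to 3 days, and missing ends set to start + 6 days.

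- If the slowest attacks are the missing ones, the imputed value still lies above the median, and the ratio is about 1.00.
- If ends are missing at random, the reported median m solves (1−q)F(m) = 0.5. The ratio is exp(0.8z), where z is the standard normal quantile of 0.5/(1−q). For q = 5%, 10%, 20% and 30% this gives 1.05, 1.12, 1.29 and about 1.57, so resolution looks slower. When one of the other two limits in 17.11 falls earlier, the lengthening is smaller.

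**With right-censoring.** Under non-informative loss as in Case 1, the Kaplan-Meier median was 0.999 to 1.005 times the true value for every q from 2% to 30%.

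**The case against.** The best reply is that the SAP excludes nothing: it says all subjects in the Full Analysis Set. That is right. A reader might infer that attacks without an event are dropped, but the text is silent, and the defect is a rule that leaves them no valid place.

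A reader might also infer that both endpoints will be biased short. For resolution the documents do not support this. SAP 17.11 may keep the attack in as an event, and the median could then be unaffected or too long. Nor do the documents show that unrecorded attacks are the slow ones. A diary entry can be missed for unrelated reasons. Protocol Table 3 and sections 7.1.4 and 7.1.5 continue attack recording to the 1-month visit, where possible also for subjects who discontinue, so leaving treatment need not lose the event.

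A harsher model, in which unrecorded attacks never improve or resolve, solves (1−q)exp(−t) + q = 0.5. At q = 10% it puts the median 15% and the upper quartile 23% short. Nothing in the documents supports that assumption.

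Nor does it follow that icatibant in particular is made to look fast. Two of the summaries run from any acute treatment and two from onset, and none has an icatibant comparator. Icatibant is also described by injection counts (SAP 10.4) and related adverse events (SAP 11.6).

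Finally, uncensored Kaplan-Meier quartiles equal the empirical quartiles the protocol planned. True, but those have the same gap.

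**Conclusion.** The point holds in a limited form. Ruling out censoring is a stated method that can give wrong quartiles, and the SAP does not define how attacks without an observed event enter. Under Cases 1 and 2 the median is too short by about 5% to 7% at q = 5% and 10% to 14% at q = 10%. Under Case 3 there is no bias. These sizes rest on assumed shares and exponential times.

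The case is firmest for initial improvement, where no rule fills the gap. For resolution the direction cannot be settled until the SAP says whether 17.11 dates are used. Those are dates without a clock time, which is a further difficulty for a time measured from an injection.

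The summaries are descriptive and outside the hierarchy in SAP 10.3, where success rests on the primary endpoint alone. This is worth correcting because it is cheap and concerns listed secondary endpoints. It does not threaten the trial's conclusion.

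**What to change.** In SAP 10.4, delete the clause that rules out censoring. Then state the following:

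- Every eligible attack enters. One without an observed event is right-censored at the last diary entry or end of observation.
- Attacks are not censored at the start of the next attack. Protocol 7.2.2.1 requires a full symptom-free day before a new attack, so the earlier one has already resolved, and censoring there would discard a known resolution.
- Further therapy is not treated as non-informative censoring, because needing it signals a slow response. Follow the attack to its recorded event and report how many attacks received further therapy.
- Say whether end dates imputed under 17.11 feed time to resolution.
- Report the number of attacks without an event for each summary.
- Record the move from the protocol's descriptive summary to Kaplan-Meier in SAP section 16.

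The cost is a few sentences and a little more programming on diary data already collected. Reported times may be somewhat longer. Right-censoring still assumes that the end of diary recording is unrelated to how the attack is going, which is why the count of attacks without an event should be shown.
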